1.2. Study Design

1.2.1. Overall Design

Study F3Z-MC-IORW (IORW) is a multicenter, open-label, controlled, single-arm pragmatic outpatient study in participants with T1D or T2D that comprises of 2 study periods, including:

- a 6-week run-in period (Study Period 1) when insulin timing and dosage data

 CCl is masked to the participant using the Glooko® Research Mobile Application (RMA) and is unmasked to the healthcare professional (HCP) using the Glooko HCP platform, and
- a 12-week intervention period (Study Period 2) when insulin timing and dosage data

[figure not shown]
 CCI is unmasked to the participant using the Glooko RMA and the HCP using the Glooko HCP platform.

Study IORW will be carried out in France and will include up to 10 clinical study sites. The study is expected to last approximately 16 months, with each participant duration of approximately 18 weeks. Approximately 50 participants will be enrolled in the study. Best efforts will be made to enroll a participant ratio of 4:1 for participants with T1D to participants with T2D.

1.2.1.1. Study Period 1 (Run-in) – Weeks 1 to 6 (Baseline)

Following the screening, the participants who meet study criteria will:

- receive sponsor-provided Humalog® Tempo™ Pen and Tempo Smart Button, Dexcom G6 Continuous Glucose Monitoring (CGM) system, and study-specific Android smartphone, and
- be instructed on how to use the study platform and will receive guidance from the study team on the use of the real time CGM data on the receiver to help them manage diabetes and insulin dosing. They will be trained on how to upload their CGM data on the Glooko RMA.

Participants will be asked to follow their pre-insulin study regimen (as prescribed by the investigators), lifestyle, and behavior. It is recommended that the site does not interact with the participant with respect to their Glooko RMA during the masked Study Period 1 unless required for participant safety. The study participant and HCP will not communicate, outside of the scheduled visit and activities, except in cases of acute complication, adverse event (AE) and device deficiency (DD) reporting, or need for technical support.

Following Study Period 1 (during Visit 3), mealtime insulin timing and dosage data

will be unmasked to the study
participant by the HCP. The study participant and HCP will then review and discuss together the
data collected during Study Period 1, including the potential reasons for suboptimal glucose
control. The HCP will be able to propose any educational activities to be taken during Study
Period 2 that would result from the review of the Glooko platform report, including insulin dose
adjustments and other advices deemed appropriate (for example, missing bolus doses, late
injection timing, and carb counting).

1.2.1.2. Study Period 2 (Intervention) – Weeks 7 to 18

Following Study Period 1, the participants will enter the 12-week Study Period 2 during which insulin timing and dosage data CCI will be visible (unmasked) to the participant and HCP in the Glooko RMA and HCP platform.

Throughout the entire Study Period 2, data from the Humalog Tempo Pen/Smart Button will be transferred to the Glooko RMA. Participants should continue to periodically upload Dexcom G6 CGM during Study Period 2.

HCPs can monitor participant adherence through the HCP portal. The participant list displays the date of last sync for each to determine the last Tempo Pen/Tempo Smart Button connection. If necessary, the study site will follow-up with participants to ensure adequate duration of CGM wear and timely Tempo Pen/Smart Button study data transfer to the Glooko RMA.

1.2.1.3. Safety Follow-up

Following completion of Study Period 2, study participants will complete their safety follow-up period.

Figure 1.1 gives an outline of the study schema.

[figure not shown]

Figure 1.1. Study schema.

2. Statistical Hypotheses

The primary objective of this single-arm study is to compare the number of missed bolus doses (MBDs) during the masked and unmasked application periods in participants with T1D and T2D via the Tempo Pen with Tempo Smart Button and on the CGM system.

The primary analyses will be conducted at the end of the clinical study on data collected from all participants.

Thus, the null hypothesis to be tested in relation to the primary endpoint is as follows:

• Study Period 2 is not different from Study Period 1 with respect to MBDs.

2.1. Multiplicity Adjustment

A p-value of \leq 0.05 will be considered statistically significant. No adjustments for multiplicity will take place.

3. Analysis Sets

For the purposes of analysis, the following analysis sets are defined:

Participant Analysis Set	Description			
Main Analysis Set	All continuous glucose monitoring (CGM) data should be included in the final analysis, but the proportion of participants who met the minimum 70% data-obtainment requirement during 14 days should be reported as part of the data completeness. Participants with ≥70% of CGM data present for a particular day will be considered complete for the day or valid CGM day. Similarly daytime and nighttime periods will be checked separately for valid CGM period. Following the guidelines of the Advanced Technologies and Treatments for Diabetes (ATTD) consensus on CGM use, only participants with at least 10 days' worth of valid CGM data out of the last 14 days (Weeks 5 and 6) in the masked application period will be considered for the main analysis set (Danne et al. 2017; Battelino et al. 2023).			
	Among these participants, only participants that satisfy the below criteria for the unmasked application period will be considered as evaluable participants and included in the main analysis set:			
	 participants with at least 20 of 28 days' worth of CGM data (Weeks 15 to 18), or participants discontinuing early that have at least 20 days' worth of CGM data in the whole unmasked application period (Weeks 7 to 18). 			
	Efficacy analyses will be carried out on the main analysis set. To allow for this clinical trial to be generalizable to the wider population and to prevent the chance of analyzing a biased set of "only adherent" participants, efficacy analyses will be repeated on the sensitivity analysis set.			
Sensitivity Analysis Set	The sensitivity analysis set includes all participants in the main analysis set, plus participants with at least 10 days' worth of CGM data in the whole masked application period (Weeks 1 to 6), and all participants with at least 20 days' worth of CGM data in the whole unmasked application period (Weeks 7 to 18).			
Safety Analysis Set	Safety analyses will be carried out on the Safety Population, which consists of all participants with at least 1 measurement in the masked application period and/or unmasked application period.			

4. Statistical Analyses

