## 7.1. Discontinuation of the Study Intervention

In rare instances, it may be necessary for a participant to permanently discontinue study intervention. If study intervention is permanently discontinued, the participant will not remain in the study to be evaluated. Participants should report AEs and DDs and complete other safety follow-up at exit visit, in accordance with this protocol. Safety follow-up should be performed as outlined in Section 1.3 (SoA), and Section 2.5 (AEs and SAEs of the protocol).

The Sponsor shall be notified of any instance of participant withdrawal or discontinuation. Any data collected up to the point of withdrawal or discontinuation may be used in the study.

See the SoA (Table 1.1) for data to be collected at the time of discontinuation of study intervention and for any further evaluations that need to be completed.

There will not be any research-related follow-up visit once their participation in the trial has ended, as the study participants will be routinely monitored as part of their diabetes management. In the event of discontinuation or early termination, participants will be contacted 3 days after they have stopped the study intervention for a remote follow-up.

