4.3.2. Main Analytical Approach

The primary endpoint is the difference in the average number of MBDs per week during the Study Period 2 (Weeks 15 to 18), compared to the Study Period 1 (Weeks 5 and 6). The average of the Week 5 average number of MBDs and Week 6 average number of MBDs will be considered baseline. The change for each of average number of MBDs of each Week 15, Week 16, Week 17, and Week 18 will then be calculated from the averaged baseline. MBD is defined as no insulin dose from 1 hour prior to through 1 hour after the start of a glucose excursion, where a glucose excursion is defined as a >70 mg/dL (>3.9 mmol/L) rise within 2 hours, not preceded by a value <70 mg/dL (<3.9 mmol/L).

The average MBDs per week will be calculated for:

- Weeks 5 and 6 for Study Period 1 (masked), and
- Weeks 15 to 18 for Study Period 2 (unmasked).

The actual MBDs and change from baseline will be summarized descriptively by study period and by week, and presented in a table.

The analyses for the primary endpoint will be conducted using a mixed-effect models for repeated measures (MMRM) using average MBD of each week (Weeks 5–6 and Weeks 15–18). The study period will be a fixed effect, baseline body mass index (BMI) and baseline HbA1c as covariates, and subject as the random effect. The repeated measure will be time, as measured in weeks (2 weeks in Study Period 1 and 4 weeks in Study Period 2 for each participant). The primary analysis will occur in the main analysis set and repeated in the sensitivity analysis set.

The MMRM model will be programmed using proc mixed in SAS Software version 9.4. The details of the model, specifically the chosen covariance structure, is subject to change based on findings during model building in SAS Software version 9.4. An unstructured covariance structure will be used to model the within-participant errors. If this structure fails to converge, the following covariance structures will be used in order until one converges:

- Toeplitz with heterogeneity
- autoregressive with heterogeneity
- compound symmetry with heterogeneous variances
- Toeplitz
- autoregressive, and
- compound symmetry without heterogeneous variances.

An example data structure excerpt regarding the primary efficacy endpoint for a hypothetical Subject 1 will be similar to Table 4.1.

Table 4.1. Data Structure Example

Usubjid	Week	StudyPeriod	BaseBMI	BaseHbA1c	Weekly Average MBD	Baseline MBD	Change in MBD

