6.2. Appendix 2: Timing of Assessments and Events for Analysis

Study Day 1 is the date in which the participants start Visit 1. Study days will be calculated as follows:

 $Pre\ first\ usage,\ study\ days = event\ date - Visit\ 1\ date$

On the day of or post data upload, study days = event date -Visit 1 date +1

The initial 4 weeks of the study will be used to allow participants to reach a routine before the baseline data assessment. Therefore, unless otherwise stated, data collected from the last 2 weeks of the masked period (Study Period 1, Weeks 5 and 6) will be used as baseline. Data from the last 4 weeks of the unmasked period (Study Period 2, Weeks 15 to 18) will be used for endpoint, in other words, 2 weeks prior to Visit 3 (face-to-face) and 4 weeks prior to Visit 7 (face-to-face) will be used. Data from these specified timepoints will be used to assess the primary and secondary objectives.

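### Participants who leave before Week 15 can count as evaluable, yet neither planned MMRM uses their missed-bolus data after unmasking

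*SAP*

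**What the plan says.** **Entry to the sets.** Under SAP Section 3 and protocol 9.2.1, the main set requires 10 CGM days in Weeks 5-6 and then one of two conditions. The first is 20 of 28 days in Weeks 15-18. The second is open only to "participants discontinuing early that have at least 20 days' worth of CGM data in the whole unmasked application period (Weeks 7 to 18". The sensitivity set takes the main set "plus participants with at least 10 days' worth of CGM data in the whole masked application period (Weeks 1 to 6", with 20 days anywhere in Weeks 7-18. Its stated purpose is to make the result more general and to avoid analysing a set tilted towards adherent people.

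**The model.** SAP 4.3.2 specifies a mixed model for repeated measures ("MMRM) using average MBD of each week (Weeks 5–6 and Weeks 15–18"). It adds: "The primary analysis will occur in the main analysis set and repeated in the sensitivity analysis set". Table 4.1 of the SAP shows the same six weeks. SAP Appendix 2 sets baseline at Weeks 5-6 and the endpoint at Weeks 15-18, and says: "Data from these specified timepoints will be used to assess the primary and secondary objectives".

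**After stopping.** Protocol 7.1 says: "If study intervention is permanently discontinued, the participant will not remain in the study to be evaluated". It also says: "Any data collected up to the point of withdrawal or discontinuation may be used in the study".

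**Other planned output.** SAP 4.3.2: "The actual MBDs and change from baseline will be summarized descriptively by study period and by week". SAP 4.2 lists the week of discontinuation, and SAP 4.8.1 explores the number of dropouts and of CGM days descriptively.

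**The concern.** The rule that makes a participant evaluable and the model that analyses them use different parts of Period 2. With daily wear, someone who leaves between Period 2 day 20 (in Week 9) and day 56 (end of Week 14) is in the main set with 0 of 4 Period 2 rows. Their 20 to 56 days of Period 2 data are not modelled, although protocol 7.1 permits their use.

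Their Weeks 5-6 rows stay in the likelihood, so dropout that depends on baseline missed bolus doses is covered. Dropout that depends on behaviour after unmasking is not, because the model never sees that behaviour. The sensitivity set does bring in intermittent wearers, but it repeats the same model and so has the same gap for these leavers. Agreement between the two sets is no evidence against this bias, and a single-arm design has no control arm to offset it.

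The main-set N can also include people with no Period 2 value. It is then not the number behind the period contrast and should not be compared with the required 24.

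**Working it through.** **1. The plan's own figure.** Protocol 9.4 gives a difference of 0.323 missed doses per day, SD 0.419, correlation 0.2, two-sided alpha 0.05 and power 80%, hence n = 24. Treating 0.419 as the per-period SD, the SD of the difference is 0.419 × sqrt(2 × (1 - 0.2)) = 0.530. A paired t-test then gives n = 24, as in Table 9.1. (Read literally as the SD of the difference, 0.419 would give 16.) Per week, 0.323 × 7 = 2.261 and 0.419 × 7 = 2.933. These anchor the simulation.

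**2. Set-up.** There are four block means (Weeks 5-6, 7-10, 11-14, 15-18), multivariate normal with SD 2.933.
- From the documents: true change -2.261; correlation of Weeks 5-6 with later blocks 0.2.
- Assumed: means of 10, then 7.739; correlation among later blocks 0.5 or 0.7; leaving at the end of Week 10 or Week 14 (28 or 56 Period 2 days, so in the main set with daily wear); logistic dropout with log-odds +1 per SD of the driver; about 10%, 20% or 34% leaving in total. The last is close to the plan's whole 35% loss allowance, so it is an upper case.
- Estimation: maximum likelihood for monotone missing data, no BMI or HbA1c, n = 2,000,000. *Planned* uses the Weeks 5-6 and 15-18 blocks. *Added* uses all four.

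**3. Estimated change per week** (true value -2.26; ranges run over later-block correlations 0.5 to 0.7):

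| Dropout driven by | Analysis | 10% | 20% | 34% |
|---|---|---|---|---|
| (a) Weeks 5-6 | planned | -2.26 | -2.26 | -2.26 |
| (b) more missed doses, Weeks 7-14 | planned | -2.39 to -2.44 | -2.52 to -2.61 | -2.69 to -2.86 |
| | added | -2.26 | -2.26 to -2.27 | -2.26 |
| (b) fewer missed doses, Weeks 7-14 | planned | -2.13 to -2.08 | -2.01 to -1.91 | -1.83 to -1.65 |
| | added | -2.26 | -2.26 | -2.26 |
| (c) unseen Weeks 15-18 values | planned | -2.52 | -2.76 | -3.11 |
| | added | -2.45 to -2.39 | -2.64 to -2.52 | -2.92 to -2.72 |

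In (a) the added model also gives -2.25 to -2.26. Relative to 2.261, the planned error in (b) is 6-8%, 11-15% and 19-27%. In (c) it is 11%, 22% and 38% as planned and about 6-9%, 11-17% and 20-29% with the added blocks. With a Weeks 5-6 correlation of 0.5 and a later-block correlation of 0.7, (b) planned gives -2.39, -2.51 and -2.69.

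**4. At the trial's size.** Scenario (b), later-block correlation 0.5, n = 50, 4000 runs (Monte Carlo SE 0.01):

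| | 10% | 20% | 34% |
|---|---|---|---|
| Planned estimate (SD) | -2.38 (0.54) | -2.51 (0.56) | -2.70 (0.61) |
| Added estimate (SD) | -2.26 (0.54) | -2.26 (0.56) | -2.26 (0.62) |
| Planned bias / SD | 0.12/0.54 = 0.22 | 0.25/0.56 = 0.45 | 0.44/0.61 = 0.72 |
| Mean number with both periods | 45 | 40 | 33 |

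The added blocks cost essentially no precision.

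**5. Sample size.** Falling below 24 of 50 with both periods needs more than 50 - 24 = 26 losses, and 26/50 = 52%. That is beyond the plan's 35%, so no shortfall is claimed.

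**The case against.** - **The text may intend these data to be used.** SAP Section 3 says that all CGM data should enter the final analysis, and both documents allow exceptions to the analysis windows. But no sentence, code or data layout supplies another window for early leavers. At best the point is unspecified.
- **Dropout was considered.** Protocol 9.3.6 lists dropouts and CGM days among the sensitivity analyses, without limiting them to description. SAP 4.8.1 makes them descriptive, so no estimate of the contrast results.
- **The size is assumed.** This stands. Nothing in the documents gives dropout timing or links it to missed doses, and protocol 7.2.2 expects discontinuation to be uncommon. The 35% also covers missing CGM data, so 34% leaving before Week 15 is extreme. In the 10% case the bias is about 0.2 of the estimate's standard deviation.
- **The added model succeeds partly by construction.** This also stands. In (b), dropout depends only on data that the model then includes. In (c), most of the bias remains.
- **Blocks replace weekly rows as well as adding weeks.** A difference from the planned result could come from either change. This calls for care in interpretation but does not remove the gap.
- **The counts are partly available.** The SAP 4.2 listing would let a reader identify early leavers, but it does not tabulate who has modelled values in both periods.

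**Conclusion.** The concern holds. Early leavers can be evaluable on Weeks 7-14 data that no planned model uses, and the sensitivity set shares this omission with the main set. The planned analysis is sound if dropout depends only on what it models. It can be biased if dropout depends on missed doses after unmasking.

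Under the stated assumptions the error is 6-8% of the effect at about 10% dropout and 11-15% at about 20%, with 19-27% as an upper case. Either direction is possible, and the actual size cannot be known from the documents. This should be corrected, mainly because the safeguard that the SAP names cannot detect the problem; it does not by itself undermine the primary analysis.

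**What to change.** 1. Keep the primary analysis on Weeks 5-6 and 15-18.
2. Add one sensitivity analysis in the sensitivity set with up to four rows per participant: the missed-bolus rate per 7 evaluable CGM days in Weeks 5-6, 7-10, 11-14 and 15-18. Use block as fixed effect, baseline BMI and HbA1c as covariates, and an unstructured covariance over the blocks. That takes 4 × 5/2 = 10 parameters; weekly rows for Weeks 5-18 would take 14 × 15/2 = 105. The contrast stays Weeks 15-18 minus Weeks 5-6. Weeks 1-4 stay out of baseline, and no day counts in two blocks.
3. For each set, report how many participants give at least one modelled value in Weeks 5-6, in Weeks 15-18 and in both. Compare the number with both, not the main-set N, with 24.

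**Cost:** one model and one count table, on data already collected. The added model still assumes missing at random given the Week 5-14 data, and only partly corrects dropout driven by unseen later values. Blocks with few evaluable days weigh the same as full ones, so report evaluable days per block.

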4.1. General Considerations

The study will use a frequentist approach to statistical analysis. Descriptive statistics for continuous variables will entail mean, standard deviation (SD), minimum, median, and maximum. Descriptive statistics for categorical variables will include frequency and percentage.

Efficacy analyses will be conducted on the Main Analysis Set and repeated on the Sensitivity Analysis Set. Safety analyses will be conducted on the safety analysis set, unless otherwise stated.

Any change in the data analysis methods described in the protocol will require an amendment only if it changes a principal feature of the protocol. Any other change to the data analysis methods described in the protocol, and the justification for making the change, will be described in the CSR. Additional exploratory analyses of the data will be conducted, as deemed appropriate.

Analysis data sets, statistical analyses and associated output generated by Lilly will be generated using SAS® Software version 9.4 or later.

4.2. Participant Dispositions

The number and percent of participants in each analysis population will be presented with percentages based on the Safety Population.

Additionally, participant allocation will be summarized in a table by investigative site for those who enter the trial.

Participant disposition will be summarized in a table by study period. Specifically, the table will include the number and percentage of participants who discontinued, and the number and percentage of participants by primary reason for discontinuation. This table will be completed in the Safety Population.

Additionally, a data listing will be generated that includes participant identification (ID), population type, and week of discontinuation.

4.3. Primary Endpoint Analysis

Efficacy analysis will be performed on the main analysis set and the sensitivity analysis set using a mixed-effect modeling strategy for repeated measures, described in Section 4.3.2. Raw CGM data will be used and derived in Analysis Data Model (ADaM) datasets to obtain the endpoints.

[figure not shown]
4.3.1. Definition of Endpoints

4.3.1.1. Missed Bolus Doses

MBDs will be identified by using the CGM (interstitial glucose values) and Tempo Smart Button data.

MBD is defined as no insulin dose from 1 hour prior to through 1 hour after the start of a glucose excursion, where a glucose excursion is defined as a >70 mg/dL (>3.9 mmol/L) rise within 2

hours, not preceded by a value <70 mg/dL (<3.9 mmol/L) (Edwards et al. 2022). If a dose between 1000 and 1100 hours would be classified as the correct or optimum time to administer the insulin dose before the 1100 hour meal, no insulin dose between 1000 and 1200 hours would be an MBD (Figure 4.1).

Abbreviation: MBD = missed bolus dose.

[figure not shown]
Figure 4.1. Missed bolus dose.

The Algorithm for identifying MBDs for each participant is as follows. Note that the algorithm will be applied to determine its adequacy, no adjustment of the algorithm will be made after the database lock.

- 1. Identify all the nadirs (Nt, t = 1, to m, m = the count of the last nadir) in the analysis period. The missed dose identification procedure starts from t = 1.
- 2. Identify missing doses associated with the nadirs:
 - i. If an increase of 70 mg/dL or more from Nt is NOT found prior or at minimum (Nt + 2 hours, Nt+1), then move to the next nadir and repeat Step 2 (no excursion occurred post Nt and prior to next nadir or Nt + 2 hours, whichever is closer to Nt),
 - ii. If an increase of 70 mg/dL or more from Nt is found prior or at minimum (Nt + 2 hours, Nt+1), then Pen data will be examined.
 - a) If there is an injection within 1 hour prior to Nt, then move to the next nadir and repeat step 2,
 - b) If there is NO injection found within 1 hour prior to Nt, and if the 70 mg/dL increase is prior to an injection after the Nt, or if there is an injection before reaching the 70 mg/dL increase but over 30 minutes after the Nt, then the number of missed dose + 1 and move to the next nadir and repeat Step 2,
- 3. Step 2 will be repeated until the end of the analysis period.

The definitions and clarification of the terms used in the algorithm:

[figure not shown]
- 1. **Nadir**: a nadir is defined as the time-point (Nt) with the lowest glucose in the time window from Nt 30 minutes to Nt + 30 minutes, inclusive (in other words, 30 minutes prior to the time-point to 30 minutes post the time-point). The first and the last nadir in the analysis period might have fewer readings prior or post the nadir respectively. The nadir must not be preceded by a hypoglycemia (<70 mg/dL) (Figure 4.2).
 - If there are 2 or more tied nadirs identified within 30 minutes, the last nadir will be the nadir in the time window.
- 2. **Date and time of injection**: among the several records (within seconds or minutes, but not more than 30 minutes) captured for each injection in the Pen data, the date and time of the last record will be used for the injection in the calculation.
- 3. **Analysis period:** the period with consecutive CGM readings (every 5 minutes) without more than 2 hours gap.
 - If the gap is more than 2 hours, a new analysis period will start from the first reading post the gap to the next gap/end of the study period. The identification will be performed in the analysis period if the duration of the analysis period is more than 2 hours, but will not be done otherwise.
- 4. Algorithm will be applied in the analysis period based on available data, without missing data imputation (in other words, the time-points with missing data will not be taken into account). However, the values of "High" and "Low" will be replaced by 401 and 39 respectively, since the CGM platform cannot provide the actual results once the glucose levels are over 400 or under 40. Any value above 400 will be reset to 401 and any value under 40 will be reset to 39 if there are any such readings.

* This condition means that the glucose levels 30 minutes before and 30 minutes after are not larger than the current (G_t)

* The check for increase in the diagram would be of 70 mg/dL.

Figure 4.2. Nadir identification diagram.

The check for increase in the diagram would be of 70 mg/dL.

Figure 4.3. Missed bolus dose identification diagram.

Based on the results of the missed bolus doses, the number of days per week with a missed bolus dose for each participant will be estimated.

For each participant the number of missed bolus doses per week in the period will be calculated using the formula:

(Total number of Missed Bolus doses / Number of Days with Evaluable CGM data) * 7

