#### 2.3.1. Commercial Devices and Products

#### 2.3.1.1. Tempo Smart Button

The Tempo Smart Button (manufactured by Lilly, Indianapolis, IN USA) is a reusable data transmitter (or data transfer module) that:

- detects and stores information from a Tempo Pen, and then
- transfers insulin dose-related data to a compatible mobile application via Bluetooth® wireless technology.

The dose-related data corresponds to the brand of insulin, dose amount, date, and time. Figure 2.2 provides an illustration of the Tempo Smart Button.

Figure 2.2. Tempo Smart Button.

The Tempo Smart Button is designed to be attached and detached from a Tempo Pen and is only functional when attached to a Tempo Pen.

When paired with an RMA, the Tempo Smart Button transmits stored data CC the RMA user interface. The Tempo Smart Button is designed so that no outside information or data can be received by the Smart Button. The communication is only in one direction: from

the Tempo Smart Button to the RMA. It is not possible to use the RMA to modify the data stored on the Tempo Smart Button.

Once the Tempo Smart Button module is paired to the RMA on the study-provided mobile device, the module will automatically transfer data to the RMA after a dose is delivered, as long as:

- the user has placed the Tempo Smart Button in the proximity of the paired mobile device
- Bluetooth is enabled on the participant's mobile device, and
- the RMA is launched and open.

If the Tempo Smart Button is not in proximity of the mobile device before Bluetooth Low Energy (BLE) shuts down, then the data will be transferred the next time that the Tempo Smart Button is activated, and the RMA is open (that is, data are not lost). The dose records, up to a total of 5840 (Tempo Smart Button IFU) remain in the Smart Button data storage for the life of the module; dose records are not deleted after transmission to the RMA.

The Tempo Smart Button to be used in this study will be the CE-marked presentation (Class I EU MDR).

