## 9.2.2. Sensitivity Analysis Set

The sensitivity analysis set includes all participants in the main analysis set, plus participants with at least 10 days' worth of CGM data in the whole masked app period (Weeks 1 to 6), and all participants with at least 20 days' worth of CGM data in the whole unmasked app period (Weeks 7 to 18).

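### Missed bolus doses are inferred from absent pen records, but only CGM completeness is required, so doses never recorded count as missed

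*SAP*

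**What the plan says.** SAP Section 4.3.1.1 identifies MBDs from two data streams, CGM and the Smart Button. Once a nadir is followed by a qualifying rise, the pen data are searched. The branch that adds to the count begins "If there is NO injection found within 1 hour prior to Nt". (It also counts some recorded injections given more than 30 minutes after the nadir; that does not affect this point.)

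Every completeness rule concerns CGM alone:

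- **Valid day** (SAP Section 3): at least 70% of that day's CGM data.
- **Main analysis set** (SAP Section 3, Protocol 9.2.1): at least 10 days "worth of valid CGM data out of the last 14 days (Weeks 5 and 6) in the masked application period", then 20 of 28 CGM days in Weeks 15–18, or 20 CGM days in Weeks 7–18 for early discontinuers.
- **Sensitivity analysis set** (Protocol 9.2.2): adds participants with at least 10 days "worth of CGM data in the whole masked app period (Weeks 1 to 6"), and those with 20 CGM days in Weeks 7–18.
- **Analysis period** (SAP 4.3.1.1): broken by CGM gaps of more than 2 hours.
- **Weekly rate** (SAP 4.3.1.1): "Total number of Missed Bolus doses / Number of Days with Evaluable CGM data) * 7".

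There is no imputation: "the time-points with missing data will not be taken into account". The algorithm is fixed at lock: "no adjustment of the algorithm will be made after the database lock".

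On the device, Protocol 2.3.1.1 says the button is "designed to be attached and detached from a Tempo Pen and is only functional when attached to a Tempo Pen". If it is out of range, "the data will be transferred the next time that the Tempo Smart Button is activated".

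**The concern.** The two data streams are treated asymmetrically. A missing CGM reading is visible and is skipped. A missing injection record looks the same as no injection and is scored as the outcome.

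The protocol itself shows how a dose can go unrecorded. The button works only while attached and must be moved to each new disposable pen (Protocol 2.3.1.1 and 2.3.1.2). It can fail or be lost. Table 6.3, footnote a, tolerates non-study rapid-acting insulin for about a week in emergencies. Protocol 9.4 allows for participants who cannot be analysed for technical reasons, but no rule defines them for the pen.

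With no concurrent arm, a change in capture between the two windows goes straight into the primary difference. Better capture in Period 2, when participants can see their dose data, would look like improved adherence. Worse capture would hide a real improvement. Equal loss in both windows only attenuates the difference.

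No planned analysis varies pen completeness. SAP 4.3.3.1 varies the MBD time window and the size of the rise. Protocol 9.3.6 and SAP 4.8.1 otherwise explore masked weeks, CGM days and dropouts.

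**Working it through.** **The plan's own figure.** Protocol 9.4 gives a difference of 0.323 MBD/day, SD 0.419, correlation 0.2, two-sided alpha 0.05 and 24 evaluable participants. Table 9.1 reproduces if 0.419 is taken as the per-period SD:

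- SD of the difference = 0.419 × √(2 × (1 − 0.2)) = 0.530/day.
- Paired t-test by noncentral t: n = 24, power 81.6%.
- Effect per week = 0.323 × 7 = 2.26.

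**Bias formula.** Let E be qualifying excursions per day, m the share truly missed, and c the share of taken doses that are recorded.

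- Observed MBD/day = E × [m + (1 − m)(1 − c)].
- With no true change, a gain g in capture gives a false fall of E × (1 − m) × g.
- Gain that imitates the whole planned effect = 0.323 / [E × (1 − m)].

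**Assumptions.** The documents give neither c nor E. Protocol 2.1.3 reports, for the cited smart-pen study, at least 25% of meals missed at 3 meals/day, and 5 missed per week. I use m = 0.25 with E = 3 and E = 1.5. A third case keeps 5/week at E = 1.5, so m = (5/7)/1.5 = 0.476. The 10-point gain is illustrative.

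For the first case, 3 × 0.75 × 0.10 = 0.225/day, and × 7 = 1.58/week. The last three columns give the chance of a significant result in the benefit direction at n = 24 (nominal 2.5%). Even loss is by noncentral t. The other two are simulated with a paired t-test: each participant loses a share L of Period 1 doses with probability g/L, where L is one half or all.

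| Case | False fall/week, g = 10 points | Gain that imitates 2.26/week | Loss even | Affected lose half | Affected lose all |
|---|---|---|---|---|---|
| E = 3, m = 0.25 | 1.58 | 14.4 points | 51% | 31% | 17% |
| E = 1.5, m = 0.25 | 0.79 | 28.7 points | 17% | 14% | 11% |
| E = 1.5, m = 0.476 | 0.55 | 41.1 points | 10% | 10% | 9% |

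**Opposite direction.** Suppose the true fall is 0.323/day and capture drops from 100% to an average of 95% in Period 2.

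- E = 3, m = 0.25: Period 2 misses are 0.75 − 0.323 = 0.427/day, so 2.573 doses/day are taken. Unrecorded doses add 0.05 × 2.573 = 0.129. The observed fall is 0.194/day = 1.36/week, and power is 31–41% across the three loss patterns.
- E = 1.5, m = 0.25: observed fall 1.75/week, power 50–60%.
- E = 1.5, 5/week held: observed fall 1.87/week, power 58–66%.

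**Equal loss.** At 90% capture in both windows, 0.323 × 0.9 = 0.291/day = 2.03/week, power 73%.

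**One participant.** Non-study insulin on 7 of 14 baseline days inflates that baseline by 3 × 0.75 × 0.5 × 7 = 7.9/week and moves the mean of 24 by 7.9/24 = 0.33/week. At E = 1.5 the figures are 3.9 and 0.16.

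**The case against.** The strongest reply is that the study already works to keep pen data complete:

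- Doses are stored on the button and transferred later, uploads are checked at visits, and sites may chase late transfers.
- The Schedule of Activities reviews pen and button use at Visit 1 and Visits 3 to 7, and device deficiencies at every visit. A replacement button can be dispensed at an unscheduled visit.
- Weeks 1–4 are set aside so that participants settle before baseline.
- App and insulin data are summarised by period (SAP 4.5.5), useable pen data are summarised (SAP Appendix 3), and an exploratory objective relates app interaction to MBD change.

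These lower the risk, and storage largely disposes of late synchronisation. None recovers a dose the button never recorded, and none changes how an MBD is counted or which days enter the rate. The CGM-only glucose endpoints and recorded insulin dose could hint at an artefact but would not correct the primary estimate.

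The objections to the magnitude stand in part. Ten points is arbitrary. The 25% is a share of meals, whereas I apply it to excursions; if bolused meals produce fewer qualifying rises, the bias is smaller. E = 3 supposes a qualifying rise at every meal, so that whole row is upper-end. E = 1.5 with m = 0.25 implies only 1.5 × 0.25 × 7 = 2.6 missed per week, against the cited 5, so the last row matters. Total loss at g = 10 points needs about 0.10 × 24 = 2.4 participants with no pen records throughout Weeks 5–6.

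It is also true that a rule based on known gaps will not find undetected or partial-day detachment.

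**Conclusion.** The concern holds. As written, the rule scores a taken but unrecorded dose as a primary-endpoint event whenever the glucose rise qualifies, and no pen-data criterion limits this. That follows from the text and needs no assumption.

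The size and direction of any bias are not established. Under the assumptions above, a 10-point gain in capture with no true change would produce a false fall of 0.55 to 1.58 MBD/week, and a false significant benefit in roughly 9% to 51% of trials. The upper figure requires 3 excursions/day and evenly spread loss. A 5-point fall in capture would cut 81.6% power to between 31% and 66%. A single participant on non-study insulin for half the baseline window would move the mean by 0.16 to 0.33/week.

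This should be fixed: the primary endpoint is exposed, the remedy is cheap, and the SAP closes the algorithm at database lock.

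**What to change.** Before database lock, amend the SAP as follows.

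1. **Define an MBD-evaluable day** as a valid CGM day not known to lack pen capture. Use recorded button loss, failure or replacement, recorded use of non-study rapid-acting insulin, and upload coverage. Upload coverage mainly catches a button lost or failed before its last read. Where only a complaint date exists (Protocol 2.5.3), bound the interval by the last and next recorded dose and the eCRF serial-number records (Protocol 6.2). Do not require a recorded dose for a day to count, since that would delete days on which every dose was truly missed.
2. **Use the same days** in the numerator, the denominator and the 10/14 and 20/28 criteria, with matching rules for the sensitivity analysis set.
3. **Add a sensitivity analysis** of the primary endpoint that also excludes days with zero recorded doses, stating that it may remove days of genuine complete omission.
4. **Report pen capture by week and period** beside the primary result: share of valid CGM days with any recorded dose, recorded doses per day, and days excluded.

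The cost is SAP wording and derivation code; the timestamps, complaint, dispensing and medication records are already collected. There will be slightly fewer evaluable days and participants. Intervals inferred from dose gaps are approximate and may take in some truly missed doses. Undetected or partial-day detachment remains and should be stated as a limitation.
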